Title: Improving Adherence in Adolescents and Young Adults with Bipolar Disorder Principal Investigator: [name] (UHCMC/CWRU) & [name] (UC)

Co-Investigators: [name], [name], [name] (UC), [name]

Version Date: May 26, 2022

Background:

This project will build upon an evidence-based adherence enhancement approach in adult BD and optimize the intervention to meet the specific developmental needs of a population (Adolescents and Young Adults- AYA with BD) for which there are no currently accepted adherence interventions and for which adherence behavior mechanisms are poorly known. This project will use a step-wise approach to characterize the needs of the target population, refine the intervention, and test mechanistic and adherence-related outcomes. This study would be the first to modify and pilot test an intervention that targets adherence barriers in order to optimize adherence in AYAs with BD. Other novel elements include: 1) using iterative qualitative input to optimize a manualized intervention salient to AYAs with BD, 2) assessing the intervention in two geographically distinct sites, and 3) examining mechanisms of adherence behavior in AYAs. The resulting feasibility, acceptability and preliminary efficacy data will lay the groundwork for an RCT with the overarching goal of enhancing generalizability and scale-up.

There is no current standard-of-care for improving adherence in AYAs with BD. An expanding literature suggests that it may be possible to enhance treatment adherence in BD.1, 2-6 Multiple-strategy interventions are likely to be more effective than a generic single-strategy intervention.⁷⁻¹⁰ However, broadly-focused psychosocial interventions that address the full scope of BD problems are not consistently associated with improved adherence. 1,11 Intensive psychosocial interventions are not practical in many clinical settings. Additionally, they are unlikely to be tolerated by non-adherent AYAs with multiple academic, employment and social commitments. 12-14 Similar to the adult BD literature, existing care approaches in AYAs with BD do not specifically target adherence and may not be practical for clinical settings. Miklowitz and colleagues have successfully used family-focused treatment (FFT) for adolescents with BD. 15, 16 However, FFT requires more than 20 sessions and a 9-month intervention duration, a time commitment that is not ideal for AYA, who tend to be oriented toward more immediate rewards. Thus, there is a clear need for brief interventions that are attractive to AYAs and which can rapidly facilitate key health behaviors.

Customized adherence enhancement is a novel intervention that works in BD. Findings from our group, as well as other adherence research 17,1,18,19,20,21-27 suggest that key modifiable adherence barriers in BD include an under-appreciation of illness severity/consequences of non-adherence, substance abuse and other high risk behaviors that impede appropriate medication-taking, difficulties with medication routines, and inadequate ability to communicate with prescribing clinicians regarding drug side-effect concerns. We developed CAE to address key barriers to medication adherence, specifically for non-adherent patients with BD.^{28, 29} Complementary and differing sources of qualitative data (focus groups, advisory board input, cognitive interviews) will optimize delivery of CAE to meet the needs of AYAs with BD.

Research in AYAs with chronic health conditions suggests that addressing adherence barriers predicts outcomes: The Pediatric Self-Management Model (Figure 2),30 developed by [name] (co-I) and colleagues. highlights the individual, family, healthcare system, and community factors that influence disease management and how these processes in turn impact adherence and health outcomes. This model has been applied to a variety of chronic conditions and shares important targets for adherence interventions, including the specific focus on barriers in the current proposal. [name] and colleagues demonstrated that a greater number of adherence barriers correlates with and predicts worse adherence in AYAs with chronic health conditions.^{31, 32} Specifically. and aligned with the CAE intervention developed by [name] and [name], BD knowledge, communication with clinicians and support systems (e.g., family, peers), risk-taking (e.g. substance abuse, unprotected sex), and medication-taking routines appear to be key mechanisms to improve adherence in AYAs. However, there is a need to incorporate the unique issues relevant to AYAs with BD when targeting adherence barriers. Qualitative findings will inform modifications which may include remote technology-facilitated delivery methods (i.e. smart phone) to appeal to AYAs.

Project Design:

Aim 1:

In Phase 1, we will conduct focus groups in adolescents and young adults (AYAs) with bipolar disorder (BD), their parents/guardians/care partners, and healthcare providers to evaluate barriers & facilitators to adherence. We will use these data, as well as input from an advisory board, to modify an adult intervention that targets adherence barriers in order to optimize adherence, Customized Adherence Enhancement (CAE), with the goal of targeting our hypothesized mechanism, such that it is developmentally specific, appropriate and acceptable to AYAs with BD.

In Phase 2, we will conduct cognitive interviews (e.g., "think aloud") with 6-8 of the AYAs with BD (ages 16-21 years) to elicit feedback on the resulting CAE-AYA.

Aim 2: In Phase 3, we will conduct a pilot randomized-controlled trial of CAE-AYA vs. enhanced treatment as usual (ETAU) to examine changes in medication adherence (primary outcome) in AYAs with BD.

Hypotheses 1: At 6 month follow-up, compared to ETAU, individuals in CAE-AYA will have greater improvement in adherence measured by the Tablets Routine Questionnaire (TRQ) and electronic adherence monitoring.

Hypotheses 2: We expect greater improvements in secondary outcomes, including health related quality of life and symptoms in CAE-AYA vs ETAU group.

Aim 3: Exploratory analyses will investigate CAE-AYA mechanistic effects by evaluating whether adherence barrier change (BD knowledge, communication with clinicians/parents/guardians/care partners, medication routines and substance use/risky behaviors) is related to adherence change.

Hypotheses 3: Change in knowledge, communication with clinicians/parents/guardians/care partners, medication routines and substance use/risk-taking behaviors will mediate improved adherence.

Number of Study Participants

We plan to enroll a total of up to 82 participants across all 3 phases and both sites (see breakdown below):

Phase 1: focus groups/advisory board (n=up to 54; all at CWRU)

Phase 2: cognitive interviews (n=up to 8; all at CWRU)

Phase 3: The total number of subjects that may be enrolled in to the RCT across both sites (CWRU and UC) is 40.

Inclusion and Exclusion Criteria

Phase 1 Focus Group/s and Advisory Board

We will conduct 2-3 focus groups in AYA with BD (6 individuals per focus group with a total of 12-18 individuals), 2-3 focus groups of parents, legal guardians or care partners (e.g., spouse, grandparent, adult sibling, etc.) who are involved in the care of and live with an AYA with BD (6 individuals per focus group with a total of 12-18 individuals), and 2-3 focus groups of healthcare providers that care for AYA with BD (6 individuals per focus group with a total of 12-18 individuals). AYA and parent/guardian/care partner focus group participants will be referred by clinicians or self-referred in response to IRB-approved advertisements. To optimize generalizability, some of the prescribing healthcare providers will be community-based.

We will then convene an advisory board (AB) of AYAs with BD (n= up to 10), parents/guardians/care partner of AYAs with BD (n= up to 10), and a group of healthcare providers (e.g., physicians, therapists, pharmacists, and nurses) that care for AYAs with BD. AYA and parent/guardian/care partner AB members will be a representative subset of the members of the focus groups. Healthcare provider AB participants will be physicians, therapists, pharmacists, and nurses that care for AYAs with BD.

Inclusion for AYA focus group and AB members

1. Individuals between the age of 16 and 21 years old.

- 2. DSM-5 diagnosis of bipolar disorder (BD)
- 3. If <18 years, able and willing to give written informed assent and have a legal guardian provide written informed consent. If > 18 years, able and willing to provide written informed consent.
- 4. Fluent in English.

Inclusion for parent/guardian/care partner focus group and AB members

- 1. Individuals of age 18 years or older.
- 2. Parent, legal guardian or other person who is closely involved with the care of and lives with an adolescent/young adult who meets the study criteria.
- 3. Willing/able to provide written, informed consent for their participation.
- 4. Fluent in English

Inclusion for provider focus group and AB members

- 1. Individuals of age 18 years or older.
- 2. Physician, therapist, pharmacist, or nurse that cares for AYAs with BD.
- 3. Willing/able to provide written informed consent for their participation.
- 4. Fluent in English

Exclusion for all focus groups and AB members

- 1. Unable to receive care in the outpatient setting due to illness severity
- 2. A DSM-5 diagnosis of an autism spectrum disorder or primary psychotic disorder.
- 3. Documented or suspected IQ< 70.

Phase 2 Usability testing and feedback:

In Phase 2, CAE-AYA will undergo usability testing and feedback with 6-8 AYAs with BD, representative of age, gender, and ethnicity. Participants will be referred by clinicians or self-referred in response to IRB-approved advertisements.

Inclusion for Phase 2 participants

- 1. Individuals between the age of 16 and 21 years old.
- 2. DSM-5 diagnosis of bipolar disorder (BD), type I or II.
- 3. Poor adherence defined as missing ≥ 20% of prescribed evidence-based BD medications, i.e., mood stabilizer (e.g., lithium, valproic acid, or carbamazepine) or second generation antipsychotics, on the TRQ at any point since being diagnoses with bipolar disorder.
- 4. If < 18 years, able and willing to give written informed assent and have a legal guardian provide written informed consent; if > 18 years, able and willing to provide written informed consent.
- 5. Fluent in English.

Exclusion for Phase 2 participants

- 1. Unable to receive care in the outpatient setting due to illness severity.
- 2. A DSM-5 diagnosis of an autism spectrum disorder or primary psychotic disorder.
- 3. Documented or suspected IQ<70.
- 4. Prior enrollment in CAE.

Phase 3 Randomized Clinical Trial:

Once a referral has been made, either by self or clinician referral, a research assistant will telephone the potential participant, give a brief description of the study, and invite them to an appointment to assess their eligibility. Individuals who provide informed consent (or assent with informed consent provided by their legal guardians if they are < 18 years old) will then proceed with screening and enrollment for the RCT.

Inclusion for RCT participants

- 1. Individuals between the age of 13 and 21 years old.
- 2. DSM-5 diagnosis of bipolar disorder (BD), type I or II as diagnosed by the Structured Clinical Interview for DSM-5 (SCID-5).

- 3. Poor adherence defined as missing ≥ 20% of prescribed evidence-based BD medications, i.e., mood stabilizer (e.g., lithium, valproic acid, or carbamazepine) or second generation antipsychotics, on the TRQ for the past week or past month.
- 4. If < 18 years, able and willing to give written informed assent and have a legal guardian provide written informed consent. If > 18 years, able and willing to provide written informed consent.
- 5. Fluent in English.

Exclusion for RCT participants

- 1. Unable to receive care in the outpatient setting due to illness severity.
- 2. A DSM-5 diagnosis of an autism spectrum disorder or primary psychotic disorder.
- 3. Documented or suspected IQ< 70.
- 4. Have recently (in the past month) started a new psychotherapy/behavioral intervention

Special/Vulnerable Populations:

Minors

The CAE-AYA intervention is meant to be an adjunct to routine clinical care. The AYA with BD participant and their legal guardians (if < 18 years) will be informed and it will be understood that acceptance or refusal to participate in any phase of the study will not influence their ability to receive clinical care at any affiliated hospital or clinic setting or elsewhere, and that they are free to withdraw from study participation at any time. The informed consent/assent process will be documented for each participant. Specifically, for all participants, it will be documented that information was provided regarding the risks, benefits, and alternatives to study participation.

Consistent with the Federal guidelines, all participants/guardians will be informed, verbally and in the written consent/assent form, of the federally mandated reporting laws for child abuse and neglect. Specifically, the consent form will read, "the state of Ohio, mandates all those working with children report suspected incidents of abuse or neglect. In addition, research records, just like hospital records may be subpoenaed by a court order. If some information about abuse is revealed that must be reported, or if a court order to release the reports is received, an attempt will always be made to inform you before the Department of Human Services or any other agency is consulted. Within the bounds of confidentiality permitted by the law, no information about you (or your child) will be shared with any individual or agency without your prior consent." Thus, except under circumstances covered under the mandated child abuse reporting laws, and/or situations in which the adolescent/young adult and/or a family member is judged to be a danger to him- or herself or others, no information about the adolescent/young adult or family will be shared with any individual or agency without prior consent.

Students/Employees

UHHS or CWRU employees or students will not specifically be recruited for this study, however, they will be allowed to participate if they fit the inclusion criteria and do not directly report to the Psychiatry Department. Students and employees may directly benefit from participation. Anyone with an employment or academic relationship to CWRU or UH will be informed that their participation in the study or refusal to do so, will in no way influence their grades, employment, or subsequent recommendations. Employees will never be made to feel that their job, promotion, salary, or status in any way depends on participation in the research study. The Principal Investigator or any other coinvestigator will not be responsible for directly recruiting and/or obtaining informed consent from any person under his or her direct supervision/employee.

Setting:

- 1) Research will be conducted at the Research offices of the PIs, [name] in Cleveland and [name] in Cincinnati
- 2) Participants will be referred by local clinicians who have been informed of the study by study staff, by self-referral in response to IRB flyers, and by email as described in the Recruitment section.
- 3) The Cleveland offices are in the W.O. Walker Center, [name].

The consent process may be conducted remotely via video conferencing, using either UH Zoom, CWRU restricted Zoom, Zoom for Healthcare or WebEx, and REDCap (individual link emailed directly to the participant/guardian) if necessary. All other study procedures may also be conducted remotely via telephone or

via video conferencing, using UH Zoom, CWRU restricted Zoom, Zoom for Healthcare or WebEx and REDCap (individual link emailed directly to the participant/guardian), if necessary.

Recruitment Methods

Participants will be recruited for Phases 1 & 2 of the study at CWRU. It is expected that most participants will be referred from the child, transitional care and the general adult psychiatry clinics in the Department of Psychiatry at CWRU/UH or (for Phase 2) be self-referred in response to IRB-approved flyers advertising the study which will be posted with permission of staff at Community Mental Health Clinics, physician offices, and other organizations serving this population. Healthcare providers will also be recruited by email for focus groups and advisory boards. Follow-up methods will include both email and phone calls.

Participants for Phase 3 of the study will be recruited from CWRU/UH and child and adult clinics in Cincinnati. Once a potential participant has been identified by their clinician, the clinician will ask if they are interested in hearing more about the study and ask permission for someone from the study team to call them. Potential participants may also self-refer in response to IRB-approved flyers advertising the study which will be posted with permission of staff at Community Mental Health Clinics, physician offices, and other organizations serving this population. Once the referral has been made, either by self or clinician referral, a research assistant will talk with the potential participant over the phone, give a brief description of the study, and invite them to an appointment to assess their eligibility.

At the CWRU site, we will recruit participants through their clinicians from the Department of Psychiatry at UHCMC, the Division of Child and Adolescent Psychiatry at UHCMC, and affiliated community mental health centers. The CWRU site will also recruit using ResearchMatch. social media ads, Google search ads and bus ads. Social media ads will be posted on Facebook originating from the main UH Facebook page. Bus ads will run on the RTA bus system. Social media ads, Google search ads and bus ads are being done in coordination with UH Marketing & Communications and Brokaw ad agency. We will also query TriNetX to identify potential participants. Address, phone numbers and email addresses will be collected so that parents/guardians/potential participants can be contacted (by letter or email, followed by a phone call). The letters will mention specifically that individuals can opt out of the follow up phone call. Potential participants/their parents/quardians who do not opt out of the follow-up phone will be contacted and, if they express interest in the study, a screening visit will be scheduled. Up to 4 attempts will be made to contact the potential participant. Research personnel will leave a voicemail if the person does not answer. For those participants who cannot be contacted, refuse participation, or otherwise do not qualify for the study, only aggregate numbers will be retained to keep track of recruitment efforts. The personal information will only be kept for as long as necessary (i.e. until the participant is enrolled or documented as a pre-screen failure). We will request a partial waiver of HIPAA to be able to collect PHI for recruitment purposes.

In Cincinnati we will recruit participants from The Mood Disorders Clinic at the University of Cincinnati Medical Center, The Division of Child and Adolescents Psychiatry at Cincinnati Children's Medical Center, and the Central Clinic Community Mental Health Center. The UC site will also recruit using ResearchMatch. We will also run an electronic medical record query at this site as well, using the same method as described above for the CWRU site.

Clinicians at the above mentioned clinics will be given information about the research study and will be asked to consider referring AYA patients of theirs with BD and ask them if they would be interested in hearing more about a research study. The research assistant will then call patients who have agreed to being called, give them a brief description of the study, and prescreen them for basic inclusion/exclusion criteria over the phone. If patients are still interested, an appointment will be made to meet with the RA in person to consent the participant and complete the screening visit.

The CWRU outpatient clinics from which we will recruit provided care to 2,212 unique individuals in 2018 who were between the ages of 14-20. Patients are seen for follow-up every 1-3 months.

The University of Cincinnati (UC) outpatient clinics from which we will recruit patients provide care to approximately 3,500 unique individuals annually. Typically, patients are seen for follow-up every 1-3 months.

Research will be conducted at the Research offices of the PIs, [name] in Cleveland and [name] in Cincinnati. Participants will be referred by local clinicians who have been informed of the study by study staff, by self-referral in response to IRB flyers, and by email as described in the Recruitment section. The Cleveland offices are in the W.O. Walker Center, [name].

Consent Process

At the CWRU site, the consenting will take place at the PI's research offices within the Department of Psychiatry in the W.O. Walker Center. The consent process may also be conducted remotely over video conferencing, using either UH Zoom, CWRU restricted Zoom, Zoom for Healthcare or WebEx, and via REDCap/electronic written consent (individual link emailed directly to the participant/guardian) if necessary. Before enrollment in the study, an authorized member of the investigational staff will explain to potential participants the aims, methods, reasonably anticipated benefits, and potential hazards of the study, and any discomfort participation in the study may entail. The research staff will present the consent form in detail, and make sure the participants understand the study by encouraging them to ask any questions they may have, and asking them to explain what the study will involve in their own words. The participant and their parent/guardian (if applicable) will be given sufficient time to read the informed consent form and the opportunity to ask questions. Participants or their parent/guardian (if applicable) will also be asked to sign a Photograph, Image and Audio Release Form.

The consent process will begin when the research assistant first talks on the phone with the potential participant and explains the study to them. If possible, potential participants (if > 18 years old), will be given a copy of the consent form ahead of time by mail or email and they will be asked to read it carefully. RCT participants will be allowed to take the consent/assent form home to think it over and schedule another time to come back to finish the screening visit if they wish.

The research staff will present the consent form in detail, and make sure the participants understand the study by encouraging them to ask any questions they may have, and asking them to explain what the study will involve in their own words. Once the researcher has confirmed the identity of the subject, the researcher, subject and their parent/guardian (if applicable) sign either a physical copy of the consent form or an electronic version of the consent form in REDCap. For those consenting via e-consent, identity will be confirmed by asking the potential participant to show his/her driver's license or if not available, any state or government-issued picture identification card. If they do not have picture identification available, they will be asked to provide the last four digits of the social security number, their date of birth and one of the following: account number, street address, insurance carrier name, insurance policy number, medical record number, birth certificate or insurance card.

At each visit the participant will be asked if they want to continue with the study. The research assistant who consents the participants will not be in any way involved with their clinical care. The AYA with BD participant and their legal guardians (if < 18 years) will be informed and it will be understood that acceptance or refusal to participate in any phase of the study will not influence their ability to receive clinical care at any affiliated hospital or clinic setting or elsewhere, and that they are free to withdraw from study participation at any time.

Research Participants who are not yet adults (children and teenagers) will parental permission be obtained from one parent even if the other parent is alive, known, competent, reasonably available, and shares legal responsibility for the care and custody of the child. Signed consent form will be documenting the parental/guardian permission. If a participant has a legal guardian, they will be allowed to sign consent for the participant. Participants who are 14-17 years old will sign the consent form and their parent will countersign it. Participants who are 13 years old will sign the assent form and informed consent from participant's parent will be obtained and documented using an IRB-approved consent.

Waiver of Written Consent for Clinicians

We will be asking the clinicians of subjects who participate in the RCT portion of the study to complete a questionnaire giving their impressions of the intervention their patient received and asking them what types of adherence improvement or support approaches are used in their clinic. When participants enroll in the study, they are asked to sign a release of information so we may talk to their treating clinician. Study staff will use that contact information to reach out to clinicians to complete this questionnaire. Clinicians will be sent a survey link via REDCap. The initial page of the RedCap survey will include an electronic consent form. Consent will be implied by completion of the survey. Alternatively, the clinician may complete their questionnaire over the phone or by having it mailed to them for them to mail back to the study site. In those cases, study staff will review with them in detail the language in the consent form that explains the purpose of the study, the procedures involved, potential risks and benefits, how to withdraw from the study, confidentiality, and informs respondents that participation is voluntary. A copy of the informed consent may be sent to the potential subject for them to review prior to consent should they request this. After reviewing the consent form with the clinician and answering any questions they may have, verbal consent will be obtained over the phone from the clinician.

Those who enroll via mail will be mailed a copy of the consent form along with their questionnaire. Clinician participation involves the completion of an online survey and involves no more than minimal risk. A survey such as this, conducted outside of the research context would not require written consent.

[figure not shown]
Study Design/Procedures

Phase 1: Investigation of AYA Needs in Adherence Promotion: Adaptation of CAE and development of new content will be guided by focus groups and key informant interviews with a representative advisory board (AB) of AYAs with BD (n= up to 10), their parents/guardians/care partners (n= up to 10), and a group of healthcare providers (e.g., physicians, therapists, pharmacists, and nurses) that care for AYAs with BD. To optimize generalizability, some of the prescribing providers will be community-based. Focus groups and AB meetings may take place in person or via a video conferencing platform with optional telephone call-in if needed.

Prior to the first AB meeting, we will conduct 2-3 focus groups in AYA with BD (6 individuals per focus group with a total of 12-18 individuals), 2-3 focus groups of parents, legal guardians or care partners who live with an AYA with BD (6 individuals per focus group with a total of 12-18 individuals), and 2-3 focus groups of healthcare providers that care for AYA with BD (6 individuals per focus group with a total of 12-18 individuals) to assess perceived adherence barriers and facilitators. Focus groups will be organized, conducted, and analyzed in the format described by Morgan and Krueger. ³⁴ All focus group participants will complete a demographics form that should take no more than 5 minutes to complete. This form will be completed either on paper or in REDCap via a survey link sent to the participants email address. The focus groups and AB will be convened at CWRU and led by [name] & [name]. All focus groups and AB meetings will be video or audio-recorded and transcribed verbatim (any reference to names or other PHI will be removed/coded to ensure deidentification) to undergo thematic analysis and reviewed by the members of the study team at CWRU, UC, Cincinnati Children's Hospital Medical Center (CCHMC), and University of Florida (UF). In the event that a participant agrees to be in a focus group, but is unable to attend the focus group because of scheduling or other problems, the study team may conduct an individual interview (either in person or by phone) following the same set of questions that would have been administered in the focus group.

Following the focus groups, the AB will meet twice. At the first meeting, we will present a summary of the perceived barriers/facilitators from focus groups and present a first draft of the CAE-AYA intervention. We will elicit additional suggestions on barriers/facilitators and receive input on the CAE-AYA draft. In the second AB meeting, we will present a revised draft and solicit input for a final product. Those participating in the AB who did not participate in a focus group portion of phase 1 will be asked to complete a demographics form that should take no more than 5 minutes to complete The resulting intervention will combine CAE elements and focus on adherence barriers within a development framework ³³ that articulates the involvement of support networks (e.g., family, peers, and clinicians), acknowledges the presence and variability of support network stress, engagement in risk-taking behaviors, and is sensitive to the needs of AYAs with BD.

Phase 2: Intervention Refinement Based on Patient Input: CAE-AYA will undergo usability testing and

feedback with 6-8 **AYAs** representative of age, gender, and ethnicity. AYA will all have self-reported difficulties with adherence (missing > 20% of BD medication at any point since being diagnosed with bipolar disorder). We will determine usability by systematically observing AYAs under controlled conditions to detect issues that can lead to lack of engagement.35 Specifically, we will evaluate the acceptability, comprehensibility, and relevance of each CAE module. Each participant will undergo a 1hour session of testing to minimize the burden of the evaluation and to ensure that each module is reviewed by 2-3 AYAs with BD.

After brief explanation by a trained facilitator, participants will be asked to 'think aloud' as they work through one

module, thus allowing us to evaluate the thought processes of the AYA as he/she works through the modules.³⁶ Sessions will be video recorded, and notes will be taken by the facilitator. Modifications will be made after each AYA completes testing, as they play a crucial role in developing the intervention content and materials. The recordings may be transcribed verbatim (any reference to names or other PHI will be removed/coded to ensure deidentification) and reviewed by the members of the study team at CWRU, UC, CCHMC, and UF. These sessions may take place in person or via a video conferencing platform with optional telephone call-in if needed

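### The RCT exclusions do not cover earlier exposure to CAE or CAE-AYA, so young people who helped develop the intervention could be randomised and may modestly dilute the arm contrast

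*Combined protocol and SAP*

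**What the plan says.** All references are to the combined protocol and SAP.

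- **Exclusion for RCT participants** has four items: illness too severe for outpatient care, autism spectrum or primary psychotic disorder, IQ below 70, and "Have recently (in the past month) started a new psychotherapy/behavioral intervention". None mentions CAE, CAE-AYA or participation in an earlier phase.
- **Exclusion for Phase 2 participants** has as its fourth item "Prior enrollment in CAE".
- **Study Design/Procedures, Phase 1**: after the focus groups, the team will "present a first draft of the CAE-AYA intervention" to the advisory board, and a revised draft at a second meeting. The board has up to 10 AYA members.
- **Study Design/Procedures, Phase 2**: in a one-hour session, "participants will be asked to 'think aloud' as they work through one" module. There are up to 8 testers.
- **Number of Study Participants** places Phases 1 and 2 entirely at CWRU. **Recruitment Methods** draws Phase 3 from CWRU/UH as well as Cincinnati.
- **Inclusion for RCT participants** begins with "Individuals between the age of 13 and 21 years old". This range contains the 16 to 21 range used for AYAs in Phases 1 and 2.
- **Control Group (ETAU)** states an aim of preventing treatment contamination. The means given is separate interventionists for the two arms.
- **Risks to Research Participants** describes taking part in the focus group, advisory board and interview activities, or else in the pilot trial.

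The Phase 3 schedule of events does not record earlier-phase participation, and it is not among the example covariates under Data Analysis.

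**The concern.** Prior exposure is treated as disqualifying in the usability phase, which has no comparator, but not in the only phase that estimates a treatment effect. The stated contamination control works through staff. It does not reach a participant who arrives already having seen the material.

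A control who has worked through a module, or reviewed the drafts, is not a clean ETAU participant. A CAE-AYA participant with the same history may have less left to gain. Either would pull the estimated difference towards zero. The trial is meant to supply preliminary efficacy data for a later RCT, so an understated effect would carry forward into that planning. Because the plan does not record exposure, the analysts could neither detect the problem nor examine it.

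**Working it through.** **1. Is the route open on the eligibility text?**

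| | AYA advisory board | Phase 2 testers | RCT |
|---|---|---|---|
| Age | 16-21 | 16-21 | 13-21 |
| Diagnosis | any bipolar disorder | type I or II | type I or II, by SCID-5 |
| Non-adherence | none required | at least 20% missed at any time since diagnosis | at least 20% missed in past week or month |
| Site | CWRU | CWRU | CWRU and UC |
| Saw CAE-AYA | two drafts | one module, one hour | not addressed |

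An earlier participant with type I or II disorder who currently misses at least 20% of doses meets the RCT criteria on these rows. The past-month exclusion would catch only a very recent session, and only if screening staff counted it as a behavioral intervention. The pool is at most 10 + 8 = 18 people, if the two groups do not overlap. Focus groups precede the first draft, so AYAs who attended only a focus group have not seen the intervention.

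**2. Reproduce the plan's power.** The Power section gives 40 randomised, up to 30% attrition, two-sided 0.05, and power 0.70 at an effect size of 0.975.

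- Completers: 40 × 0.70 = 28, or 14 per arm.
- Noncentrality: 0.975 × √(14 × 14 / 28) = 0.975 × √7 = 2.58, on 26 degrees of freedom.
- Noncentral-t power: 0.6997, which agrees with 0.70.

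**3. Illustrate dilution.** Let *s* be the share of controls exposed and *f* the fraction of the CAE-AYA benefit each carries. Then

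d_eff = 0.975 × (1 − s × f).

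This assumes the same share among completers, an unchanged standard deviation, and that exposed CAE-AYA participants end with the same benefit as unexposed ones. The documents give neither *s* nor *f*. Example: 4 of 20 with f = 0.5 gives 0.975 × (1 − 0.20 × 0.5) = 0.878.

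Each cell shows d_eff and power with 14 per arm:

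| Exposed controls | f = 0 | f = 0.25 | f = 0.5 |
|---|---|---|---|
| 1 of 20 | 0.975; 0.700 | 0.963; 0.689 | 0.951; 0.678 |
| 2 of 20 | 0.975; 0.700 | 0.951; 0.678 | 0.926; 0.655 |
| 4 of 20 | 0.975; 0.700 | 0.926; 0.655 | 0.878; 0.609 |

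With 1:1 allocation, 4 exposed controls imply about 8 exposed people randomised out of a pool of at most 18. The bottom row is therefore a high scenario.

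**4. The enrolment total.** The plan says "We plan to enroll a total of up to 82 participants across all 3 phases and both sites". The phase maxima sum to 54 + 8 + 40 = 102, which is 20 more. Counting only one RCT arm gives 54 + 8 + 20 = 82.

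**The case against.** The strongest reply is that the phases were meant to be separate and that any leak would be small.

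*Separate tracks.* The either/or description under Risks to Research Participants does point that way. It stands as a sign of intent. But it describes participant burden; it is not a criterion that screening staff apply, so it does not close the gap.

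*Small exposure.* This largely stands. One hour on one of four modules, or two draft-review meetings, is far from four core sessions, a booster, a call and active pillbox reminders. Exposure also precedes baseline, the primary outcome is change in adherence, and entrants must still be non-adherent. Many earlier participants would not qualify: the advisory board has no adherence threshold, Phase 2 accepts past non-adherence, and some will pass 21 before Phase 3 opens.

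Three stronger readings are tempting, and the documents do not support them.

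- A reader might infer from 82 against 102 that re-enrolment is planned. At most 8 of the 20 excess places could be overlap between Phases 1 and 2, so at least 12 of CWRU's 20 RCT places would have to go to earlier participants. A counting slip (54 + 8 + 20 = 82) is at least as plausible.
- A reader might infer that, because the Phase 1 and 2 route exists only at CWRU, site and treatment become confounded. Randomisation is stratified by site and the analysis adjusts for site, so exposure is balanced between arms in expectation.
- A reader might let exposed controls carry the whole benefit. With 4 of 20 that gives d = 0.78 and power 0.51, but so limited an exposure does not justify the assumption.

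Finally, this is a feasibility-oriented pilot whose power is offered only as a reference. That limits the severity of the point without removing it.

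**Conclusion.** The omission is real: as written, the plan admits AYAs who have already seen CAE-AYA, or who were previously enrolled in CAE, and has no means of identifying them. The consequence is a possible modest dilution of the arm contrast. It is not an imbalance between arms or a confounding of site with treatment.

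Its size cannot be derived from the documents. Under the assumed ranges (1 to 4 of 20 controls exposed, 0 to 50% of the benefit carried), power at d = 0.975 lies between 0.70 and 0.61. With 2 exposed controls carrying a quarter of the benefit, it is 0.68. This is a cheap improvement to the design rather than a flaw that threatens the trial. The mismatch in the enrolment total is a separate inconsistency and is not evidence of overlap.

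**What to change.** Add one item to the RCT exclusions: prior enrollment in CAE, or participation as an AYA in the Phase 1 advisory board or Phase 2 usability testing. AYAs who attended only a focus group remain eligible.

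The cost is one eligibility line and at most about 18 CWRU candidates, fewer once the other RCT criteria are applied. That site needs 20 RCT participants. Its clinics saw 2,212 people aged 14 to 20 in 2018, though not all with bipolar disorder, and it also recruits through other channels. The sample size and stated power do not change.

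If enrolment has begun, record prior exposure for every randomised participant and run a sensitivity analysis without those exposed.

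Separately, reconcile the stated total of 82 with the phase maxima of 102, and state explicitly whether a person may take part in more than one phase.
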